4.2. Per Protocol Set (PP)

The Per Protocol Set will be a subset of the Full Analysis Set and will include all subjects who completed all study evaluation periods, received 1 dose injection of NH002 and had no major protocol deviations.

4.2.1. Major Protocol Deviations

The protocol deviations defined in Protocol Deviation Handling Plan¹ (PDHP) Version 1.0 will be recorded. All protocol deviations will be discussed between CRO (Medical Monitor, Data Manager, Biostatistician) and the Sponsor and classified as “minor” or “major”. Major protocol deviations leading to the exclusion of a patient from the PP Set will be discussed between CRO (Medical Monitor, Data Manager, Biostatistician) and the Sponsor. Protocol Deviations will be assessed prior to database lock.

4.3. Safety Set (SS)

The Safety Set (SS) will consist of all subjects receiving at least 1 injection of NH002.

5. Statistical Analyses

5.1. General Considerations

The safety and efficacy variables of each dose of NH002 will be presented using descriptive statistics. For continuous variables, the descriptive statistics (N, mean, standard deviation, median, minimum, and maximum) will be presented for safety variables, and the descriptive statistics (N, mean, standard deviation, median, minimum, maximum, and 95% CI) will be presented for efficacy variables. For categorical variables, the number and percentage of subjects in each category will be presented. Data will be summarized for each dose group and overall.

All data processing, summarization, and analyses will be performed using SAS Version 9.4.

5.1.1. Baseline Definition

For each analysis, the baseline value will be a non-missing value obtained from each assessment before dosing on Day 1. If baseline data is missing no derivation will be performed and will be set to missing.

5.2. Participant Dispositions and Demographics

5.2.1. Disposition of Subjects

The following subject data will be summarized and presented:

- Number of subjects screened for overall
- Number of subjects re-screened for overall
- Number of subjects received injection for each dose group and overall
- Number and percentage of subjects who received injection completed the study phase
- Number and percentage of subjects who received injection did not complete the study phase
- Number and percentage of subjects in each analysis set.
- Number and percentage of the reason for subjects excluded from PP analysis set.
- Number and percentage of Major Protocol Deviations leading or not leading to exclusion from PP.
 - Table 01.1: Summary of Subject's Disposition, All Screened Subjects
 - Table 01.2: Incidence of Major Protocol Deviations, All Screened Subjects
 - Listing 01.1: Subject's Disposition, All Screened Subjects
 - Listing 01.2: Discontinued Patients, All Screened Subjects
 - Listing 01.3: Inclusion/Exclusion Criteria Not Met, All Screened Subjects
 - Listing 02: Protocol Deviations, All Screened Subjects

- Listing 03: Exclusion from Analysis Population, Safety Set

5.2.2. Demographic and Other Baseline Characteristics

Demographic and baseline characteristics include age, sex, height, weight, BMI and subjects with suboptimal LVEBD. Age, sex, and height will be collected once at screening visit, and weight will be measured twice at screening visit and before dosing on Day 1. The baseline weight will be the measurement on Day 1. The Body Mass Index (BMI) will be derived by weight at baseline and height. These variables data will be summarized by each cohort and overall for the SS, the PP and the FAS population.

Age=(Date of ICF signed-Date of Birth)/365.25, rounded down to the integer.

BMI (kg/m²)=Body Weight (kg)/(Height (cm)/100)², rounded to the first decimal place.

Descriptive statistics (n, mean, standard deviation, median, minimum, and maximum) will be presented for continuous variables and the number and percentage of subjects in each category will be presented for categorical variables. No formal testing of demographic or baseline characteristics will be performed.

The number and percentage of subjects with at least one medical history will be tabulated by each dose group and overall. The medical history will be summarized by system organ class and preferred terms in Medical Dictionary for Regulatory Activities (MedDRA) Version 22.0. Also, medical history data will be listed with start date and ongoing at the start of study drug.

- Table 02.1.1: Summary of Demographics and Baseline Characteristics, Safety Set
- Table 02.1.2: Summary of Demographics and Baseline Characteristics, Per Protocol Set
- Table 02.1.3: Summary of Demographics and Baseline Characteristics, Full Analysis Set
- Table 02.2: Summary of Medical History, Safety Set
- Listing 04.1: Demographics and Baseline Characteristics, All Screened Subjects
- Listing 04.2: Medical History, All Screened Subjects

5.2.3. Concomitant Medication

Concomitant medication will be listed by subject identity, drug name, indication, dose, unit, frequency, route, start date and end date.

- Listing 05.1: Concomitant Medications, All Screened Subjects

5.2.4. Exposure

The study drug administration will be listed by subject identity, dosing date, drug activation time, start dosing time, end dosing time and study drug dose.

- Listing 05.2: Study Drug Administration, Safety Set

5.3. Primary Endpoints Analysis

This is a Phase 1 study to evaluate the safety and tolerability of 3 ascending doses of NH002. Therefore, the primary endpoints are all safety assessment.

All safety assessments, including Treatment Emergent Adverse event (TEAEs), physical examination findings, vital signs (VS), clinical laboratory evaluations, other laboratory evaluations, oxygen saturation and electrocardiograms (ECGs) where indicated, will be presented using descriptive statistics for each dose of NH002. Data will be summarized for each dose group and overall.

5.3.1. Adverse Events

Adverse events recorded before injection, during injection and imaging, and post-injection. Treatment emergent adverse events (TEAEs) are those with start date on or after dosing or those worsen after dosing.

If the minutes of onset time is missing and the onset date and hour of onset time are on or after that of dosing date, the adverse event will be considered as a TEAE.

If the onset time is missing and the onset date is on or after that of dosing date, the adverse event will be considered as a TEAE.

If the onset date is a partial date (month/year) and month/year occurs on or after that of dosing date, the following cases will be considered:

- If month/year of the onset date is greater than the month/year of dosing date, the adverse event will be considered as a TEAE;
- If month/year of the onset date is equal to the month/year of dosing date, and the stopped date is on or after dosing date, the adverse event will be considered as a TEAE;
- If month/year of the onset date is equal to the month/year of dosing date, and the stopped date is a partial date, the adverse event will be considered as a TEAE.

For safety analyses, the number and percentage of subjects with at least one TEAE will be tabulated by each dose group and overall. The TEAEs will be summarized by system organ class and preferred terms in Medical Dictionary for Regulatory Activities (MedDRA) Version 22.0. Similar summaries will also be provided for related TEAEs, serious TEAEs, treatment related serious TEAEs, TEAEs that lead to death and institution of concomitant medication.

For the summary of TEAEs by severity, if a subject experienced more than one episode of an adverse event, the subject is counted only once within a preferred term by using the most severe episode. If a subject experienced more than one adverse event within a system organ class, the subject is counted once for each preferred term and once for the system organ class.

The related TEAEs which are defined as the causal relationship in “Very Likely/Certain”, “Probably”, and “Possible” will also be summarized by each dose group and overall.

- Table 03.1.1: Overview of Treatment Emergent Adverse Events, Safety Set
- Table 03.1.2: Summary of Treatment Emergent Adverse Events, Safety Set
- Table 03.1.3: Summary of Treatment Emergent Adverse Events with Severity, Safety Set
- Table 03.1.4: Summary of Related Treatment Emergent Adverse Events, Safety Set
- Table 03.1.5: Summary of Treatment Emergent Adverse Events Leading to Death, Safety Set
- Table 03.1.6: Summary of Treatment Emergent Serious Adverse Events, Safety Set
- Table 03.1.7: Summary of Related Treatment Emergent Serious Adverse Events, Safety Set
- Table 03.1.8: Summary of Treatment Emergent Adverse Events Institution of Concomitant Medication, Safety Set
- Table 03.2.1: Listing for Treatment Emergent Adverse Events Leading to Death, Safety Set
- Table 03.2.2: Listing for Treatment Emergent Serious Adverse Events Safety, Set
- Table 03.2.3: Listing for Treatment Emergent Adverse Events Institution of Concomitant Medication, Safety Set
- Listing 07: Adverse Events All Screened Subjects

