8.2.1 Visit 2: Day 1, Dosing

8.2.1.1 Before Dosing

The following procedures will be performed **before** administration of the NH002 contrast injection on Day 1:

- Eligibility: Assess against the inclusion and exclusion criteria
- Medical history, including baseline signs and symptoms should be documented and continually reassessed throughout the study
- VS: Measurements include BP, body temperature, HR, and RR
- Weight (kg)
- Standard 12-lead ECG
- Focused PE: A focused PE will include cardiopulmonary (observation, palpation, percussion, auscultation) and skin (turgor, pallor, cyanosis, erythema, lesions) assessments.
- Both a urine and a serum (β -HCG) pregnancy test are required for WoCBP before dosing on Day 1. (Note that at screening, only a urine or serum test is necessary; before dosing on Day 1, both tests are necessary.)
- Complete blood count (CBC) to include hematocrit (HCT), hemoglobin (Hgb), white blood cell (WBC) count with differential, absolute neutrophil count (ANC), and platelet count (PLT)
- Coagulation studies: Thrombin time (TT) and activated partial thromboplastin time (aPTT)
- Metabolic panel: Metabolic panel evaluations to include sodium, potassium, chloride, calcium, magnesium, phosphorus, glucose, blood urea nitrogen (BUN), creatinine, total protein, albumin, alkaline phosphatase (ALP), ALT, AST, total bilirubin, and bicarbonate
- Cardiac troponin I
- Pulse oximetry: SpO₂
- Pretreatment AEs: Baseline events, findings, and conditions before NH002 initiation should be documented and continually reassessed throughout the study.

- Concomitant medications and procedures: Concomitant medications and procedures will continue to be recorded.

8.2.1.2 5 Minutes Before Dosing

The following procedures will be performed approximately **5 minutes before** dosing:

- Imaging should proceed as specified in [Section 7.1.1](#).
- Modified 12-lead ECG monitoring should be conducted, from 5 minutes before dosing to 10 minutes after dosing. See [Section 9.1.2.2.7](#).
- Pulse oximetry: SpO₂ should be measured and recorded, from 5 minutes before dosing to 10 minutes after dosing.
- VS: BP, body temperature, HR, and RR should be measured and recorded, from 5 minutes before dosing to 10 minutes after dosing.
- Record any AEs that may occur and any changes in concomitant medication.

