9.1.2 Safety Assessments

Each subject must be carefully monitored for the development of any AEs throughout the study from the signing of the ICF to at least 7 days after receipt of the study agent (ie, Day 7 Follow-up call). Safety evaluations will also be assessed and recorded at specified time points: before injection, during injection and imaging (beginning approximately 5 minutes prior to and continuing until 10 minutes after injection), and up to 7 days post-injection.

Safety parameters to be evaluated will include:

- Standard 12-lead ECGs assessed pre-injection, and at 10, 30, and 60 minutes post-injection; during imaging, a standard 12-lead ECG will be conditionally performed at the

earliest time point when any clinically significant ECG changes indicative of arrhythmia or S-T segment change are identified within 10 minutes after injection from the modified 12-lead ECG monitoring; each standard 12-lead ECG assessment will be scored as either normal or abnormal;

- Changes in VS assessed pre-injection, during injection and imaging (beginning approximately 5 minutes prior to and continuing until 10 minutes after), and at 30, 60, and 120 minutes post-injection; VS measurements will include body temperature, HR, RR, and BP;
- The following parameters will be included in the *complete* PE (at screening): General appearance, skin (turgor, pallor, cyanosis, erythema, lesions), head (including ear, eyes, nose, and throat), neck, lungs and heart (observation, palpation, percussion, auscultation), abdomen, back lymph nodes, extremities, and a neurological exam. A *focused* PE (after screening) will include cardiopulmonary (observation, palpation, percussion, auscultation) and skin (turgor, pallor, cyanosis, erythema, lesions) assessments; each PE assessment will be scored as either normal or abnormal;
- Changes in hematology and metabolic laboratory parameters taken pre-injection and 60, 120, and 240 minutes post-injection;
- TT and aPTT pre-injection and 60, 120, and 240 minutes post-injection;
- Cardiac troponin I pre-injection and 240 minutes (4 hours) post-injection;
- SpO₂ assessed pre-injection, during injection and imaging (beginning approximately 5 minutes prior to and continuing until 10 minutes after), and at 30, 60, and 120 minutes post-injection;
- The assessment of any potential adverse allergic reactions during and post-injection.

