9.1.2.2 Adverse Events

Adverse Event Definition

An AE is defined as any untoward medical occurrence in a clinical study subject administered a medicinal product which does not necessarily have a causal relationship with this treatment. An AE can therefore be any unfavorable and unintended sign (including an abnormal laboratory finding), symptom, or disease temporally associated with the use of a medicinal (investigational) product, whether or not it is related to the medicinal (investigational) product. This includes an exacerbation of pre-existing conditions or events, intercurrent illnesses, drug interaction or the significant worsening of the indication under investigation that is not recorded elsewhere in the CRF under specific efficacy assessments. Anticipated fluctuations of pre-existing conditions, including the disease under study, that do not represent a clinically significant exacerbation or worsening need not be considered AEs.

It is the responsibility of the investigator to document all AEs that occur during the study. Any AEs will be elicited by asking the subject a nonleading question, for example, "Have you experienced any new or changed symptoms since we last asked/since your last visit?". All AEs should be reported on the appropriate page of the CRF.

Assessment of Severity

Each AE will be assigned a category by the investigator as follows:

Mild: An AE that is easily tolerated by the subject, causes minimal discomfort,

and does not interfere with everyday activities.

Moderate: An AE that is sufficiently discomforting to interfere with normal everyday activities; intervention may be needed.

Severe: An AE that prevents normal everyday activities; treatment or other intervention usually needed.

If there is a change in severity of an AE, it must be recorded as a separate event.

Assessment of Causality

Every effort will be made by the investigator to assess the relationship of the AE, if any, to the study agent. Causality should be assessed using the categories presented in the following:

Unrelated: Clinical event with an incompatible time relationship to study agent administration, and that could be explained by underlying disease or other drugs or chemicals or is incontrovertibly not related to the study agent.

Unlikely: Clinical event whose time relationship to study agent administration makes a causal connection improbable, but that could plausibly be explained by underlying disease or other drugs or chemicals.

| | |

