|----------------------|---|
| Possible: | Clinical event with a reasonable time relationship to study agent administration, but that could also be explained by concurrent disease or other drugs or chemicals. |
| Probable: | Clinical event with a reasonable time relationship to study agent administration, and is unlikely to be attributed to concurrent disease or other drugs or chemicals. |
| Very Likely/Certain: | Clinical event with plausible time relationship to study agent administration, and that cannot be explained by concurrent disease or other drugs or chemicals. |

Action Taken

The investigator will describe the action taken (with regard to the study agent and/or the subject) in the appropriate section of the CRF, as follows:

- None
- Study agent stopped
- Study agent temporarily interrupted
- Concomitant medication
- Other, specify.

Follow-up of Adverse Events

All investigators should follow up subjects with AEs until the event is resolved or until, in the opinion of the investigator, the event is stabilized or determined to be chronic. Details of AE resolution must be documented in the CRF.

Subjects should also be followed up 3 days (+3) and 7 days (+3) after receiving NH002 (ie, Day 4 and Day 7), and any AEs that occur during this time should be reported according to the procedures outlined in this section.

Documentation and Reporting of Adverse Events

All AEs should be reported and documented in accordance with the procedures outlined in this section. All AEs occurring during the study must be documented on the relevant CRF pages. The following data should be documented for each AE:

- Description of the symptom event
- Classification of 'serious' or 'not serious'
- Severity
- Date of first occurrence and date of resolution (if applicable)
- Action taken
- Causal relationship
- Outcome of event (unknown, recovered, not yet recovered, recovered with sequelae, death [with date and cause reported])

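### A recorded pre-dose adverse event that only improves after dosing can be counted as treatment-emergent, because severity-change records have no defined start date and no link to the event they continue

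*SAP*

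**What the plan says.** **Recording.** Protocol 9.1.2.2, under Assessment of Severity, states: "If there is a change in severity of an AE, it must be recorded as a separate event". The rule covers a fall in severity as well as a rise.

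**Pre-dose events.** Protocol 9.1.2 has AEs monitored "throughout the study from the signing of the ICF to at least 7 days after receipt of the study agent". Protocol 8.2.1.1 lists, among the steps before the injection, "Pretreatment AEs: Baseline events, findings, and conditions before NH002 initiation should be documented and continually reassessed throughout the study". SAP 5.3.1 also acknowledges AEs recorded before the injection. So an AE record can be open at dosing and be re-graded afterwards.

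**Dates.** The data to be documented for each AE in Protocol 9.1.2.2 include "Date of first occurrence and date of resolution (if applicable". Neither document says which start date a record opened for a severity change should carry.

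**Classification.** SAP 5.3.1 states: "Treatment emergent adverse events (TEAEs) are those with start date on or after dosing or those worsen after dosing". The two limbs are alternatives, so meeting the first is enough.

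**Summaries.** Under SAP 5.3.1, "the number and percentage of subjects with at least one TEAE will be tabulated by each dose group and overall". For the severity table, where a subject has repeated episodes, "the subject is counted only once within a preferred term by using the most severe episode".

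**An exemption.** The AE definition in Protocol 9.1.2.2 allows expected ups and downs of a condition the subject already had to go unrecorded, provided they are not a clinically significant worsening.

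**The concern.** The recording rule and the classification rule sit in different documents and do not fit together. Take a subject who reports a moderate headache after consent, has it recorded as an AE, and still has it at the injection. An hour later it is mild. The protocol calls for a second record, graded mild. If that record starts when the grade changed, the first limb of the SAP definition makes it a TEAE, although all that happened after NH002 was an improvement.

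The second limb suggests this was not intended: it would hardly be needed unless a pre-dose event was meant to qualify only by getting worse.

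TEAE reporting is the first component of the primary endpoint in SAP 1.4. The cohorts are small, and SAP 1.3 confirms that there is no placebo or active control against which to judge background events. Protocol 10.6 also uses safety in choosing a dose. A count that mixes recoveries with new or worsened events is harder to interpret in that setting.

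**Working it through.** The plan gives no figure on this point, so there is nothing to reproduce. The check applies the written rules to each possible change of grade and then sizes the effect of one affected subject.

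**1. Inputs.** Separate record on any severity change (Protocol 9.1.2.2); TEAE definition (SAP 5.3.1); three grades, mild, moderate and severe (Protocol 9.1.2.2); 12 subjects per cohort and 36 in all (Protocol 10.8).

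**2. Classification.** The AE starts before dosing, is ongoing at dosing, and changes grade afterwards. The linked rule compares the new grade with the last pre-dose grade.

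| Change after dosing | New record starts at the change: first limb | New record keeps original onset: first limb | Linked rule |
|---|---|---|---|
| moderate to mild | TEAE | not a TEAE | not a TEAE |
| severe to moderate | TEAE | not a TEAE | not a TEAE |
| severe to mild | TEAE | not a TEAE | not a TEAE |
| mild to moderate | TEAE | not a TEAE | TEAE |
| mild to severe | TEAE | not a TEAE | TEAE |
| moderate to severe | TEAE | not a TEAE | TEAE |

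With the change date as start, the first limb captures all six changes, and the second adds nothing for changes recorded this way. With the original onset as start, the first limb captures none. The three worsenings then depend on the second limb, which needs one record compared with another, and the documents state no link for doing so.

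**3. Does another rule remove the improving record?**
- The missing-time and partial-date rules in SAP 5.3.1 deal with incomplete onset data and do not test the direction of change.
- The once-per-preferred-term rule acts on records already classed as TEAEs and makes no comparison with pre-dose severity.
- The AE data items in Protocol 9.1.2.2 include no parent-event identifier.
- The exemption for pre-existing conditions reduces what is recorded in the first place. It does not reclassify an AE already recorded between consent and dosing.

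**4. Size.** If k subjects have an improving record as their only TEAE, incidence rises by k/n.
- k = 1: 1/12 = 8.3 points in a cohort; 1/36 = 2.8 points overall.
- k = 2: 2/12 = 16.7 points; 2/36 = 5.6 points.

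**5. How likely is at least one?** The documents give no frequency, so the per-subject probability p is an assumption, with subjects taken as independent. The formula is 1 − (1 − p)^n.

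| Assumed p | Cohort, n = 12 | Overall, n = 36 |
|---|---|---|
| 1% | 11.4% | 30.4% |
| 3% | 30.6% | 66.6% |
| 5% | 46.0% | 84.2% |
| 10% | 71.8% | 97.7% |

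**The case against.** The strongest reply is that no text gives the new record a post-dose start. The protocol asks for the date of first occurrence. If sites carry the original onset forward, an improving event never meets the first limb, and the second limb has a real job. This stands as a limit: the over-count depends on the start date entered. It does not clear the plan, because on that reading worsening has no stated derivation. Sites in a multicenter study could also follow different conventions.

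Second, few events may be exposed. The exemption for pre-existing conditions keeps many fluctuations out of the AE data, and baseline signs and symptoms are also taken under medical history. The screening list in Protocol 8.1.1 has no AE item, and the AE row of the schedule appears to begin five minutes before dosing, though the extracted table layout may be unreliable. This too stands. A reader might infer that the error grows with how ill a cohort is at entry; the exemption means the documents do not support that.

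Third, the consequences are limited. The analysis is descriptive, with no hypotheses. Related TEAEs are tabulated separately, and an improving record enters that table only if rated at least possibly related. Listing 07 covers AEs for all screened subjects, so a reader could trace pre-dose records. The error is also in the inclusive direction. All of this is fair, but a listing does not correct the incidence tables, and counting a recovery as an event adds no safety information.

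Finally, CRF completion guidelines or table shells may already link the records. They were not available, so the gap is shown only for the protocol and SAP.

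**Conclusion.** The concern holds in conditional form. Read together, the two rules allow an AE that was recorded after consent, was ongoing at dosing and then only improved to be counted as a TEAE. This happens if the severity-change record starts on the date of the change, which is the natural reading of a separate event but is not stated. On the other reading, improvements escape, but a genuine worsening has no defined route into the tables. Either way, SAP 5.3.1 needs a rule.

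The size is 8.3 points in a cohort and 2.8 points overall for each affected subject with no other TEAE. How many subjects would be affected cannot be told from the documents.

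Two stronger readings are not supported. A reader might infer that every improving pre-dose event will be counted, with a large inflation of TEAE rates; the start date is not fixed and no frequency is given. A reader might also infer that the dosing stopping criteria could be triggered falsely. Protocol 7.5.1.2 rests on SAEs at least possibly related to the agent and on listed clinically significant toxicities. It does not use the TEAE definition.

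**What to change.** **Protocol 9.1.2.2 or the CRF guidelines.** Keep a separate record for every severity change, so that the severity history is preserved. Add an identifier linking each such record to its parent event, and state that the record's start is the date (and time, on the dosing day) of the change.

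**SAP 5.3.1.** Add a sentence to this effect: a record opened for a severity change is a TEAE only if the parent event began on or after dosing, or if the record's severity exceeds the severity at dosing, taken as the last pre-dose grade.

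The comparator should be the last pre-dose grade and not the worst one. An event that was severe, eased to mild before the injection and became moderate afterwards has worsened after dosing, and the SAP's second limb now counts it; comparison with the worst pre-dose grade would drop it. The last pre-dose value also matches the baseline in SAP 5.3.3, 5.3.5 and 5.3.6 for vital signs, physical examination and ECGs.

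**Cost.** One link field on the AE page, one sentence in each document, and slightly more programming. No further data are needed from subjects. Under the new rule, worsening after dosing still counts and improvements do not.
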